## Patients excluded from analysis

Patients excluded from safety analysis and those excluded from efficacy analysis will be listed in tabular form with their reason for exclusion.

## 8.2.2. Patient characteristics and treatment history

Patient characteristics and treatment history will be summarized according to Section 8.1 with respect to the following factors:

• Patient Characteristics

For the following factors, summarization will be performed using the SAS and efficacy analysis set:

- Sex [male, female]
- Age (continuous)
- Age [<15 yrs., ≥15 to <65 yrs., ≥65 yrs.]
- Body weight (continuous)
- Body weight [ $\leq 50 \text{ kg}, \geq 50 \text{ to } \leq 60 \text{ kg}, \geq 60 \text{ kg}$ ]
- BMI [<18.5, ≥18.5 to <25.0, ≥25]
- Past treatment with this drug [present, absent, unknown]
- Setting of clinical practice [hospitalization, outpatient]
- History of pregnancy during study period [present, absent, unknown]

## PFIZER CONFIDENTIAL

- Target disease [TTR-FAP, other (TTR-FAP developing after domino liver transplantation)]
- Duration of disease (continuous)
- Duration of disease [<1 year,  $\geq$ 1 to <5 yrs.,  $\geq$ 5 to <10 yrs.,  $\geq$ 10 yrs.]
- Onset age (continuous)
- Onset age [<50 yrs.,  $\geq 50$  yrs.]
- Testing of mutant genotype [performed, not performed/unknown]
- Mutant genotype 1 [only V30M, V30M + non-V30M, only non-V30M, non-V30M + non-V30M, no mutation]
- Karnofsky performance status [100, 90, 80, 70, 60, 50, 40, 30, 20, 10]
- Karnofsky performance status [100-80, 70-50, 40-10]
- Family history of TTR-FAP [present, absent, unknown]
- Origin of patient [endemic region (Nagano Pref., Kumamoto Pref., Ishikawa Pref.), non-endemic region, unknown]
- Past history of organ transplantation [present, absent, unknown]
- Past history of liver transplantation [present (domino liver transplantation, after onset of FAP (incl. onset time unknown)), absent, unknown]
- Timing of liver transplantation (time from onset of FAP) [domino liver transplantation, ≤5 years after onset of FAP, >5 years after onset of FAP, time from onset of FAP to liver transplantation unknown]
- Hepatic impairment [absent, present (mild, moderate, severe, severity unknown), unknown]
- Renal impairment [absent, present (mild, moderate, severe, severity unknown), unknown]
- Baseline total NIS score (continuous)
- Baseline total NIS score [ $<70, \geq 70$ ]
- Baseline NIS-LL score (continuous)
- Baseline NIS-LL score [ $\leq 10$ , >10 to  $\leq 20$ , >20]
- Baseline TQOL score (continuous)
- Baseline TQOL score [ $\leq 20$ ,  $\geq 20$  to  $\leq 40$ ,  $\geq 40$ ]
- Severity of disease [Stage 1 (walking ability: 0-2), Stage 2 (3a, 3b), Stage 3 (4), undetermined]

For the following factors, summarization will be performed using the SAS:

- Disposition of non-V30M mutations [different non-V30M mutations (multiple counting allowed)]
- Method of diagnosis [clinical symptoms, tissue biopsy (amyloid deposition), tissue biopsy (immunohistological staining), TTR genotype, clinical symptoms + tissue biopsy (amyloid deposition), clinical symptoms + tissue biopsy (immunohistological staining), clinical symptoms + TTR genotype, tissue biopsy (amyloid deposition) + tissue biopsy (immunohistological staining), tissue biopsy (amyloid deposition) + TTR genotype, tissue biopsy (amyloid deposition) + TTR genotype, clinical symptoms + tissue biopsy (amyloid deposition) + TTR genotype, tissue biopsy (amyloid deposition) + tissue biopsy (immunohistological staining), clinical symptoms + tissue biopsy (amyloid deposition) + TTR genotype, clinical symptoms + tissue biopsy (immunohistological staining) + TTR genotype, clinical symptoms + tissue biopsy (immunohistological staining) + TTR genotype, clinical symptoms + tissue biopsy (immunohistological staining) + TTR genotype, clinical symptoms + tissue biopsy (immunohistological staining) + TTR genotype, clinical symptoms + tissue biopsy (immunohistological staining) + TTR genotype, clinical symptoms + tissue biopsy (amyloid staining) + TTR genotype, clinical symptoms + tissue biopsy (amyloid staining) + TTR genotype, clinical symptoms + tissue biopsy (amyloid staining) + TTR genotype, clinical symptoms + tissue biopsy (amyloid staining) + TTR genotype, clinical symptoms + tissue biopsy (amyloid staining) + TTR genotype, clinical symptoms + tissue biopsy (amyloid staining) + TTR genotype, clinical symptoms + tissue biopsy (amyloid staining) + TTR genotype, clinical symptoms + tissue biopsy (amyloid staining) + TTR genotype, clinical symptoms + tissue biopsy (amyloid staining) + TTR genotype, clinical symptoms + tissue biopsy (amyloid stainin

deposition) + tissue biopsy (immunohistological staining)+ TTR genotype, undetermined/unknown]

As for mutant genotype, summarization will be performed only in patients with diagnosis of mutant genotype.

## • Others

Summarization will be performed according to Section 8.1 for the following aspects:

- Disposition of concomitant medications (Concomitant medications are defined as drugs recorded in Concomitant Drug Therapies or Pretreatments Used for Target Disease [including NSAIDs etc.] that were used in the period from the start of the treatment with this drug to the discontinuation/end of the treatment. If the treatment with this drug continued exceeding the end of observation, drugs used by the last visit should be eligible.)
- Disposition of concomitant non-drug therapies (Concomitant non-drug therapies are defined as therapies recorded in Concomitant Non-Drug Therapies that were used in the period from the start of the treatment with this drug to the discontinuation/end of the treatment. If the treatment with this drug continued exceeding the end of observation, therapies used by the last visit should be eligible.)
- Disposition of pretreatments (Pretreatments are defined as pretreatments used for target disease [including NSAIDs etc.] or drugs recorded in Concomitant Drug Therapies that were administered before the start of the treatment with this drug.)

Using the SAS, the following aspects of patients will be summarized in terms of n and proportion by system organ class (SOC) and by preferred term (PT):

- Past medical history (diseases or syndromes recorded as "past history" in the medical history)
- Complications (diseases or syndromes recorded as "current history" in the medical history)

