7.2.4. Observation period

3 years from the first day of treatment with this drug (156 weeks) However, the observation period for patients who started to receive this drug after May 2018 will be 1.5 years (78 weeks).

> Pfizer Confidential Page 12 of 37

If the treatment with this drug is discontinued during the observation period, the observation period will be until the day of discontinuation. If the dose of this drug is changed for the treatment of ATTR-CM, the observation period will be up to the date of last dose of 20 mg.

This study will be conducted using booklet type CRF.

The safety and efficacy assessments will be performed at the first visit (including the end date of the observation period) on or after the end date of the observation period (day of discontinuation if the treatment is discontinued during the observation period or date of the last dose of 20 mg if the dose was changed for the treatment of ATTR-CM). However, if a subject is lost to follow-up halfway through, the safety and efficacy assessments will be performed using the information on the last visit date.

Booklet No.	Observation period	
Booklet 1	First day of treatment to Week 78 (1.5 years)	
Booklet 2	Week 79 to Week 156 (3 years)	

7.3. Registration items and study items This study will be conducted according to the following schedule of observation.

Table 1. Schedule of observation

			Booklet 1		Book	det 2
Item	Registr ation form	At start of the study	Week 52 (1 year)	Week 78 (1.5 years)	Week 104 (2 years)	Week 156 (3 years)
Information to identify the subject			-	-	-	-
First day of treatment with this drug			-	-	-	-
Presence or absence of having received/used this drug at other sites, and if Yes, patient's duration of treatment	•					
THAOS registration status/THAOS registration ID						
State of concurrent medical examination	-					→
Background variables	-		-	-	-	-
History of previous treatment drugs for the targeted disease	-	•	-	-	-	-
Targeted drug use record	-	•				>
Concomitant therapy (drug therapy/ non-drug therapy)	-	•				
General tests (height, body weight, pulse, blood pressure)	-	•				
Clinical laboratory tests	-	•				→
Plasma concentration of tafamidis (to be performed only for patients with severe hepatic impairment)	-					•
Cardiovascular evaluation (ECG, echocardiography)	-					
Assessment of neurological function (NIS)	-		-		-	
Quality of Life (QOL-DN)	-		-		-	
Ambulatory state	-		-		-	

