7.3.2.7. Concomitant therapy

7.3.2.7.1. Drug therapy

For all drugs used from the first day of treatment with this drug until the end of the observation period (or date of discontinuation of treatment with this drug), enter the information on administration (e.g., name of drug [product name], route of administration, dose, duration of treatment, and presence or absence of any action taken for adverse events). Also, enter drugs administered for the treatment of adverse events.

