#### 5.4. Subgroups

Subgroup analyses for safety and efficacy will be performed with respect to the following factors:

- Patient characteristics
  - Sex [male, female]
  - Age [ $<15 \text{ yrs.}, \ge 15 \text{ to } <65 \text{ yrs.}, \ge 65 \text{ yrs.}$ ]
  - Body weight [ $\leq 50 \text{ kg}$ ,  $\geq 50 \text{ to } \leq 60 \text{ kg}$ ,  $\geq 60 \text{ kg}$ ]
  - BMI [<18.5, ≥18.5 to <25.0, ≥25]
  - Onset age [ $\leq 50$  yrs.]  $\geq 50$  yrs.]
  - Duration of disease [ $\leq 5$  yrs.]  $\geq 5$  yrs.]
  - Past treatment with this drug [present, absent]
  - Mutant genotype 2 [with V30M, without V30M]

- Karnofsky performance status [100-80, 70-50, 40-10]
- Family history of TTR-FAP [present, absent]
- Origin of patient [endemic region, non-endemic region]
- Past history of organ transplantation [present, absent]
- Past history of liver transplantation (including for purposes other than the treatment of target disease) [present (including domino liver transplantation), absent] \* Only for safety assessment
- Past history of liver transplantation other than domino liver transplantation [present, absent (including domino liver transplantation)] \* Only for efficacy assessment
- Hepatic impairment [present, absent]
- Hepatic impairment [absent, mild, moderate, severe]
- Renal impairment [present, absent]
- Baseline total NIS score [ $\leq 70$ ,  $\geq 70$ ]
- Baseline NIS-LL score [ $\leq 10$ , >10 to  $\leq 20$ , >20]
- Baseline total QOL (TQOL) score [ $\leq 20$ , >20 to  $\leq 40$ , >40]
- Severity of disease [Stage 1 (walking ability score 0-2), Stage 2 (walking ability score 3a/3b),
   Stage 3 (walking ability score 4)]

Subgroup analysis for mutant genotype will be performed only in patients with a diagnosis of mutant genotype.

- Others
  - Pretreatment (loperamide) [present, absent]
  - Pretreatment (prednisolone) [present, absent]
  - Pretreatment (rosuvastatin) [present, absent]
  - Pretreatment (NSAIDs) [present, absent]
  - Duration of treatment [ $\leq 52$  weeks, >52 to  $\leq 104$  weeks, >104 to  $\leq 156$  weeks, >156 weeks]
  - Concomitant medication (loperamide) [present, absent]
  - Concomitant medication (prednisolone) [present, absent]
  - Concomitant medication (rosuvastatin) [present, absent]
  - Concomitant medication (NSAIDs) [present, absent]

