#### 8.1.3. Binary variables

For binary variables, patients falling into each binary category will be summarized in terms of n and proportion. When a confidence interval (CI) is determined for a proportion, the two-sided 95% CI (exact method) will be determined.

When a comparison for proportion is made between subgroups, the risk ratio (RR) and its 95% CI will be presented.

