#### **Details of adverse reactions**

Adverse reactions will be summarized in terms of n and proportion by each of the following factors:

- Seriousness [serious, non-serious]
- Known/unknown [known, unknown]
- Action taken [permanent discontinuation, temporary discontinuation or dose reduction, dose increase or no change]
- Outcome [not recovered, recovered with sequelae, improved, resolved/recovered, unknown]

Multiple adverse reactions of the same PT occurring in the same patient will be handled as follows:

- Seriousness: If both serious and non-serious reactions of the same PT occurred in the same patient, the patient will be counted as one with serious reaction.
- Known/unknown: If both known and unknown reactions of the same PT occurred in the same patient, the patient will be counted as one with unknown reaction.
- Action taken: If multiple actions were taken for adverse reactions of the same PT, only one category of action will be adopted with "permanent discontinuation", "temporary discontinuation or dose reduction", and "dose increase or no change" being given priority in this order.
- Outcome: The outcome for the last event will be adopted.

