## 8.2.3.3. Subgroup analyses

The number and proportion of patients who experienced at least 1 adverse reaction will be tabulated by factor specified in Section 5.4. The evaluation specified in Section 8.1.3 will be performed to evaluate the relationship between patient characteristics and the onset of adverse reactions. In the calculation of risk ratio, the categories to be used as the reference are underlined.

Hepatotoxicity will also be evaluated in the same manner as above if it occurs at a sufficient incidence in the evaluation.

The evaluation specified in Section 8.1.3 will be performed for infection with the presence or absence of liver transplant as a factor.

The number and proportion of patients with adverse reactions will be tabulated by SOC and PT by history of liver transplant. Events related to blood disorder in particular will be examined based on the tabulation results

The number and proportion of patients with adverse reactions will be tabulated by SOC and PT for each category of age [< 15 years,  $\ge$  15 to < 65 years,  $\ge$  65 years], hepatic impairment [Yes, No], and renal impairment [Yes, No]. The number and proportion of patients with adverse reactions in the subgroup of hepatic impairment [severe] will also be tabulated by SOC and PT.

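### Adverse-reaction risk ratios for concomitant drugs count any use on treatment, so the reaction itself can decide the exposure group and bias the ratio in either direction

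*SAP*

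**What the plan says.** SAP 5.4 lists four concomitant-drug factors, each present or absent with absent as the reference. The first is "Concomitant medication (loperamide)"; the others are prednisolone, rosuvastatin and NSAIDs. SAP 8.2.3.3 tabulates patients with at least one adverse reaction by every 5.4 factor and states: "The evaluation specified in Section 8.1.3 will be performed to evaluate the relationship between patient characteristics and the onset of adverse reactions". SAP 8.1.3 supplies the measure: "When a comparison for proportion is made between subgroups, the risk ratio (RR) and its 95% CI will be presented". Hepatotoxicity, the major investigation item, is handled the same way if it is frequent enough.

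The one visible definition of concomitant medication is in SAP 8.2.2 (Others): recorded drugs "that were used in the period from the start of the treatment with this drug to the discontinuation/end of the treatment". If treatment runs past the end of observation, use up to the last visit counts.

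Two further provisions matter:
- Protocol 7.3.2.7.1 puts drugs given for adverse events in the same CRF record: "Also, enter drugs administered for the treatment of adverse events". It also collects "presence or absence of any action taken for adverse events" for each drug, an item the SAP does not use in the exposure rule.
- Protocol 7.2.4 ends follow-up with treatment: "If the treatment with this drug is discontinued during the observation period, the observation period will be until the day of discontinuation". SAP 8.2.3.1 recognises that reactions can end treatment: "Action taken [permanent discontinuation, temporary discontinuation or dose reduction, dose increase or no change".

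**The concern.** A risk ratio of this kind is meaningful only if the exposure group is settled without reference to the outcome. Here it is not, for two main reasons.

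1. **Treatment of the reaction.** A patient not taking the drug who receives it because of a reaction is counted as exposed, with the reaction then counted against the drug. This pushes the ratio above 1. It is plausible for loperamide, prednisolone and NSAIDs and unlikely for rosuvastatin (a judgement; the documents are silent).
2. **Early closure of the window.** A patient who stops because of a reaction has less time to start any other drug, so reactors drift into the unexposed group. This pulls the ratio below 1.

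A third path is unequal follow-up, from discontinuation for other reasons or the 78-week rather than 156-week observation period. Patients followed longer have more time both to start a drug and to react, which pushes the ratio up.

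The net direction is unknown and may differ by drug. A reader could see an interaction that does not exist or miss one that does. These ratios belong to the final analysis supporting the re-examination application (SAP 3).

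**Working it through.** **Size of the study.** The only size figure in the documents is the estimated number of patients. It reproduces: 0.87 × 127.54 = 110.96 and 1.1 × 127.54 = 140.29, stated as about 111 to 140. The documents also cite about 130 patients treated per year. I use N = 130, and 111 as the lower case.

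**Assumed inputs.** The documents give none of these rates.
- r = 0.30, reaction risk
- u = 0.20, use on day 1
- s = share of otherwise unexposed reactors given the drug for the reaction
- d = share of reactions that stop treatment
- The drug has no effect, so the true ratio is 1.

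**Step 1: treatment of the reaction only (no new starts, no stopping).**

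Risk if present = r(u + (1−u)s) / (u + r(1−u)s). Risk if absent = r(1−s) / (1−rs). The 95% CI uses the usual standard error of the log risk ratio at the expected counts.

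| s | Present | Absent | Ratio | CI, N=130 | CI, N=111 |
|---|---|---|---|---|---|
| 0.05 | 9.36/27.56 | 29.64/102.44 | 1.17 | 0.64–2.14 | 0.61–2.25 |
| 0.10 | 10.92/29.12 | 28.08/100.88 | 1.35 | 0.77–2.37 | 0.73–2.48 |
| 0.20 | 14.04/32.24 | 24.96/97.76 | 1.71 | 1.02–2.87 | 0.97–2.99 |

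(Counts shown are for N = 130.)

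Over a grid of r (0.2, 0.3, 0.4), u (0.1 to 0.5 in steps of 0.1) and s (0.05, 0.1, 0.2, 0.3), the expected CI excludes 1 in 15 of 60 cells at N=130 and 12 of 60 at N=111. None of these has s of 0.05 or 0.10.

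**Step 2: add unrelated new starts and stopping.** Let 20% of day-1 non-users start the drug for other reasons over 3 years at a constant rate, with reaction onset uniform over the 3 years. Drugs first given after stopping do not count.
- Exposed by the end of 3 years: 0.2 + 0.8 × 0.2 = 0.36. This applies to non-reactors.
- Exposed before a uniformly distributed onset: 0.2 + 0.8 × (1 − 0.2/(−ln 0.8)) = 0.2 + 0.8 × 0.1037 = 0.283. This applies to reactors who stop.
- Reactors who continue: 0.36 + 0.64s, which is 0.424 at s = 0.10.
- All reactors: E = 0.283d + (0.36 + 0.64s)(1−d).
- Ratio = [0.3E/(0.3E + 0.7 × 0.36)] / [0.3(1−E)/(0.3(1−E) + 0.7 × 0.64)].

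At s = 0.10:

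| d | E | Risk present | Risk absent | Ratio |
|---|---|---|---|---|
| 0 | 0.4240 | 0.3354 | 0.2784 | 1.21 (1.205 unrounded) |
| 0.3 | 0.3817 | 0.3124 | 0.2928 | 1.07 |
| 0.5 | 0.3535 | 0.2962 | 0.3021 | 0.98 (CI 0.57–1.70 at N=130) |
| 0.7 | 0.3253 | 0.2791 | 0.3112 | 0.90 |

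At d = 0.5, s = 0, 0.05 and 0.20 give 0.89, 0.93 and 1.08. With s = 0.20 and no stopping the ratio is 1.44 (0.86–2.42). If new starts are spread uniformly instead of at a constant rate, results move by about 0.01.

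**Step 3: unequal follow-up alone.** A separate simulation (20% reaction risk, 10% day-1 use, nobody treated with the drug for a reaction, no reaction-driven stopping) gives 1.12 with 30% dropout and 30% new starts over 3 years, and 1.32 with 50% and 50%.

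**Step 4: alternatives under the same null.**
- Use on day 1: 1.00 under the Step 2 model and 1.01 under unequal follow-up.
- Time-varying use, cut at first reaction: crude rate ratio 1.02 under the Step 2 model. The small excess arises because reaction hazard and drug use both rise with time; comparing within intervals of time since start gives 1.00.
- Use begun before onset, treated as a fixed group: reactors 0.283 and non-reactors 0.36 exposed, so 0.2520/0.3244 = 0.78. This is biased, because reaction-free patients have longer to become exposed.

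**The case against.** **The strongest case is about weight.** The SAP has no hypotheses or decision rules, and these are crude secondary subgroup ratios. Overall adverse-reaction incidence, the protocol's major safety analysis, is untouched. With 5% or 10% of reactors treated, no grid cell has an expected CI that excludes 1. With both main paths running at 10% treated, the ratio stays within 0.90 to 1.21, well inside the null CI of 0.52 to 1.93 for 26 exposed of 130. The 1.71 case needs 20% treated, no new starts and no stopping. All of this stands and limits the consequence.

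**Dilution.** The CRF records drugs for any adverse event, while the outcome is the subset judged related. If 10% or 20% of day-1 non-users receive the drug for an unrelated event, the 1.35 falls to 1.26 or 1.21. It does not return to 1.

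**Inference.** The definition sits under a descriptive summary, 8.2.3.3 speaks of patient characteristics while 5.4 lists these drugs under a separate heading, and a redacted block follows 8.2.3.3. So one can say only that no visible rule orders use against onset. That the ratios are intended is clear: the version 10.0 revision entries name the drugs for subgroup analysis, set the reference and remove a statement that ratios would not be calculated for them.

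**Existing safeguards.** None reaches the problem. The exclusion of drugs used after the last dose (SAP 8.2.3.1) belongs to a counts-only table and addresses neither main path. The pre-analysis check on medications (SAP 8.2.4.7) is in the efficacy section and concerns which drugs to analyse. Protocol 7.9 covers confounding from incomplete background data; this bias arises with complete data.

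**Overlap.** The pretreatment factors in 5.4 are already fixed before the first dose, so a day-1 rule partly repeats them. This is a real cost of the preferred fix.

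**Conclusion.** The concern holds. As written, the concomitant-drug ratios let the reaction determine exposure, so they do not cleanly evaluate a relationship with onset. The direction is not fixed. Under the stated assumptions and a true ratio of 1, the expected ratio ranges from 0.89 (none treated, half of reactions stopping treatment) to 1.71 (20% treated, no stopping, no new starts), and unequal follow-up can add to it. The actual size cannot be derived from the documents. It would be nil for a drug whose use is all in place on day 1. The damage is to interpretation of a limited set of descriptive ratios, including hepatotoxicity if it is analysed. The correction is cheap and should be made.

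**What to change.** For the 8.2.3.3 risk ratios only, classify a concomitant drug as present if it was in use on the first day of treatment with this drug and is not flagged as given for an adverse event. Alternatively, analyse use as time-varying up to first reaction onset, accounting for time since start of treatment. Do not use a fixed group defined by use begun before onset. Keep the any-time definition for the descriptive tables.

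The cost is SAP wording and one derivation from the drug treatment periods and the adverse-event-action item already on the CRF. The day-1 rule leaves fewer exposed patients (26 of 130 in the example), does not assess drugs started later and partly overlaps the pretreatment factors. The time-varying option avoids the last two drawbacks but adds a model to a descriptive plan. Neither removes confounding by indication. Duration of treatment, in the same 5.4 list, can also be shortened by a reaction; this change does not cover it, and its ratios need a separate caution.
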